Congestive heart failure	Clinical evidence of CHF AND either LVEF < 40% or reduction in LVEF below 55% with a drop in LVEF from	Hold CFZ	Control of clinical CHF, and return of LVEF to ≥ 40% or (if held due to drop below LVEF of 55% with > 20%	Resume CFZ at one dose decrement

Carfilzomib for Treatment of cGVHD

	prior baseline by > 20%		drop from baseline) return of LVEF to within 15% of baseline value If improvement defined above is not met	
				Discontinue CFZ therapy
Other non-hematologic toxicity \geq Grade 3	Other non-hematologic CFZ-related \geq Grade 3 toxicity not listed individually elsewhere	Hold CFZ	Resolved or back to baseline	Resume CFZ at one dose decrement
Pulmonary Hypertension	Grade 3 or 4	Hold CFZ	Resolved or returned to baseline	Resume CFZ at one dose decrement
Pulmonary Complications	Grade 3 or 4	Hold CFZ	Resolved or returned to baseline	Resume CFZ at one dose decrement
Hepatic toxicity	Grade 3 or 4 elevation of transaminases, bilirubin, or other liver abnormalities	Hold CFZ Follow LFT	Resolved or returned to baseline	Resume CFZ at one dose decrement

Carfilzomib for Treatment of cGVHD

*CBC – Frequency of CBC monitoring after holding dose for toxicity is directed by treating clinician's judgment, and not mandated by this protocol. A recommended guideline is weekly until return to baseline.

*LFT – Frequency of LFT monitoring is directed by treating clinician's judgment, in keeping with note above regarding CBC monitoring.

Permissible dose decrements:

- 36mg/m² → 27mg/m²
- 27mg/m² → 20mg/m²
- 20mg/m² → 15mg/m²
- If toxicity persists or reoccurs requiring dose reduction below 15mg/m², then carfilzomib therapy should be discontinued. No more than three dose reductions will be permitted in an individual subject on study. If toxicity continues or recurs after three dose reductions, carfilzomib therapy should be discontinued.
- If toxicity requiring dose reduction occurs on the first dose (i.e. 20mg/m²), only one dose decrement will be possible to 15mg/m². If toxicity persists or recurs on the 15mg/m² dose, carfilzomib therapy should be discontinued.

Conditions not requiring dose reduction:

- Grade 3 nausea, vomiting or diarrhea (unless persisting > 3 days despite treatment with anti-emetics or anti-diarrheals)
- Grade 3 fatigue (unless persisting continuously for >14 days)
- Alopecia
- Hyperglycemia attributed to steroids

Persistent toxicity for 3 weeks after withholding CFZ therapy:

- If the patient has toxicity attributable to carfilzomib that does not return to baseline or reach < grade 1 in severity by 3 weeks, carfilzomib therapy will be discontinued

Patient tolerates decreased dose following dose reduction for toxicity:

- If the patient tolerates the decreased dose x 2 cycles, full-dose CFZ (i.e. 36mg/m²) should be resumed on subsequent cycles.

- If subsequent toxicity occurs as defined above, the stated rules for dose reduction apply, but a second attempt to resume full-dose therapy should not be made.

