	20mg/m2 (n=26)	36mg/m2 (n=9)	45mg/m2 (n=9)	56mg/m2 (n=10)
Cmax (ng/mL)	985 +/- 641	1795 +/- 957	1902 +/- 884	2513 +/- 1527
AUC last (hr*ng/mL)	385 +/- 253	690 +/- 365	862 +/- 363	1018 +/- 416
AUC inf (hr*ng/mL)	387 +/- 255	691 +/- 368	864 +/- 366	1025 +/- 424
T ½ (hr)	1.0 +/- 0.5	1.2 +/- 0.8	1.1 +/- 0.2	1.2 +/- 1.0
CL (L/hr)	146 +/- 87	123 +/- 54	129 +/- 54	124 +/- 43

Pharmacodynamic analysis demonstrated an increased inhibition of proteasome chymotrypsin-like activity (CT-L) and all 3 subunits of immunoproteasome (LMP7, MECL1, LMP2) with higher doses of carfilzomib compared to the 20mg/m2 dose.

Summarizing current evidence from phase Ib and II trials with carfilzomib, the following are the most commonly reported **AE** (among those occurring in $\geq 20\%$ of patients): fatigue (55.9%), nausea (43.2%), anemia (42.2%), dyspnea (35.1%), diarrhea (33.8%), thrombocytopenia (32.7%), pyrexia (32.1%), cough (26.8%), headache (26.4%), upper respiratory tract infection (25.4%), vomiting (23.4%), peripheral edema (22.8%), lymphopenia (22.4%), back pain (21.5%), constipation (21.1%), and increased creatinine (20.7%).

Summarizing current evidence from phase Ib and II trials with carfilzomib, the following are the most commonly reported **SAE** (among those occurring in $\geq 1\%$ of patients), regardless of causality: pneumonia (8.1%), disease progression (5.9%), acute renal failure (3.4%), pyrexia (3.4%), congestive heart failure (2.8%), dyspnea (2.7%), pathological fracture (1.6%), hypercalcemia (1.5%), spinal cord compression (1.3%), anemia (1.1%), dehydration (1.1%), sepsis (1.1%), mental status changes (1.0%), and pulmonary embolism (1.0%).

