4.2 Exclusion Criteria

Concurrent Conditions:

1. Evidence of recurrent or progressive underlying malignant disease
2. Pregnant or lactating females
3. Surgery within 21 days prior to enrollment
 - a. Does not include placement of venous access device, bone marrow biopsy, GVHD diagnostic biopsy, or other routine procedures in chronic GVHD or post-transplantation care
4. Uncontrolled infection within 14 days prior to enrollment
 - a. Infection treated with appropriate antimicrobial therapy and without signs of progression/treatment failure does not constitute an exclusion criterion
5. Documented human immunodeficiency virus (HIV) infection
6. Active hepatitis B or C infection
7. Documented unstable angina or myocardial infarction within 6 months prior to enrollment, NYHA Class III or IV heart failure, uncontrolled angina, severe uncontrolled ventricular arrhythmias, sick sinus syndrome, or electrocardiographic evidence of acute ischemia or Grade 3 conduction system abnormalities (unless subject has a pacemaker), LVEF $<$ 40%, history of torsade de pointe,
8. Uncontrolled hypertension or uncontrolled diabetes within 14 days prior to enrollment
 - a. Sustained systolic blood pressure $>$ 160 or diastolic blood pressure $>$ 100 despite medical therapy; sustained blood sugar $>$ 300 despite medical therapy
 - b. Chronic hypertension or diabetes on appropriate medical therapy does not constitute an exclusion criterion
9. Non-hematologic malignancy within the past 3 years with the exception of:

Carfilzomib for Treatment of cGVHD

- a. adequately treated basal cell carcinoma, squamous cell skin cancer, or thyroid cancer
- b. carcinoma in situ of the cervix or breast
- c. prostate cancer of Gleason Grade 6 or less with stable prostate-specific antigen levels
- d. cancer considered cured by surgical resection or unlikely to impact survival during the duration of the study

10. Significant neuropathy per CTCAE ver. 4.03 or current version (Grade 3 and above, or Grade 2 with pain) within 14 days prior to enrollment
11. History of allergy to Captisol® (a cyclodextrin derivative used to solubilize carfilzomib)
12. Contraindication to all available HSV/varicella prophylactic antiviral drugs
13. Pleural effusions requiring thoracentesis, or ascites requiring paracentesis, within 14 days prior to enrollment

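### The heart-failure dose-hold row is ambiguous for a patient who meets both LVEF criteria, and its wording permits an easier restart after a deeper fall

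*Combined protocol and SAP*

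**What the plan says.** The CHF row of the table in section 6.2 holds carfilzomib when there is clinical evidence of CHF together with either of two LVEF findings: "LVEF < 40% or reduction in LVEF below 55% with a drop in LVEF from" "prior baseline by > 20" percent. Call LVEF under 40% limb 1, and LVEF under 55% with a fall of more than 20% limb 2.

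The resume cell asks for "Control of clinical CHF, and return of LVEF to ≥ 40% or (if held due to drop below LVEF of 55" percent with a fall of more than 20%) "return of LVEF to within 15% of baseline value". If this is met, carfilzomib restarts one dose level lower. If it is not met, carfilzomib is discontinued.

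Two general rules in the same section also apply. Treatment stops for "toxicity attributable to carfilzomib that does not return to baseline or reach < grade 1 in severity by 3 weeks". A patient who tolerates a reduced dose for two cycles goes back to 36 mg/m². Section 1.2.4 lists "congestive heart failure (2.8" percent among serious adverse events in earlier carfilzomib trials, regardless of causality.

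**The concern.** The two limbs overlap, and the row does not say which resume test governs a patient who meets both. With 'or' between the tests, a site can take the 40% test as enough for that patient. A patient with a smaller fall, who meets limb 2 only, can be held to the stricter recovery test. The patient with the worse cardiac event is then the one allowed back on drug sooner.

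The row also does not say whether 20% and 15% are LVEF points or relative change, which affects the decision to hold as well as the restart. This is a multi-center trial, so two sites could treat the same patient differently on the same echocardiogram. What is at stake is patient safety and consistent dosing. The primary endpoint and the sample size are untouched.

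**Working it through.** The plan gives no figure to reproduce here, so the check applies the row to cases.

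**Inputs.** The 40%, 55%, 20% and 15% limits come from section 6.2. Section 4.2 excludes LVEF under 40%, so baseline B is at least 40%. The plan gives no baseline distribution; B from 40% to 75% is an assumed range.

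**Formulas.** Limb 2 applies when LVEF is under 55% and also under B − 20 (points) or 0.80 × B (relative). The within-15% threshold is B − 15 (points) or 0.85 × B (relative).

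**How often the limbs overlap.** Any LVEF under 40% also meets limb 2 when B is at least 60% in points (60 − 20 = 40) or at least 50% relative (0.80 × 50 = 40). For patients with ordinary baselines who fall below 40%, meeting both limbs is the usual case.

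**Example, B = 65%.** Limb 2 applies below 65 − 20 = 45% (points) or 0.80 × 65 = 52% (relative). The within-15% threshold is 65 − 15 = 50% or 0.85 × 65 = 55.25%. A fall to 44% meets limb 2 only. A fall to 38% meets both.

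| Reading of the resume cell | LVEF needed after fall to 44% | LVEF needed after fall to 38% |
|---|---|---|
| Fully literal 'or': 40% enough for everyone | 40% (already met when held) | 40% |
| Tests matched to limbs, 40% enough if both met | 50% or 55.25% | 40% |
| Parenthesis governs every limb 2 patient | 50% or 55.25% | 50% or 55.25% |
| Both tests required (the fix) | 50% or 55.25% | 50% or 55.25% |

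Only the second reading inverts. The gap is 50 − 40 = 10 points or 55.25 − 40 = 15.25 points. On the first and second readings the patient who fell to 38% restarts at 40%. That is 25 points (25/65 = 38%) below baseline and still inside the LVEF range of limb 2.

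**Range of the inversion on the second reading.** It needs a limb-2-only band at or above 40%.
- Points: B − 20 must exceed 40, so B is above 60%. For whole-number B from 61% to 75% the gap runs from 46 − 40 = 6 to 60 − 40 = 20 points.
- Relative: 0.80 × B must exceed 40, so B is above 50%. If limb 2 means a fall through 55%, B starts at about 55%, and the gap runs from 46.75 − 40 = 6.75 to 63.75 − 40 = 23.75 points at B = 75%.

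**Effect of scale on the hold.** With clinical CHF, B = 65% and LVEF 48%, the fall is 17 points (no hold) but 17/65 = 26% relative (hold).

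**Frequency.** Assume the 2.8% CHF rate carries over to this population. Then 20 × 0.028 = 0.56 cases are expected, and the chance of at least one is 1 − 0.972^20 = 43%. At an assumed 1% it is 18%, and at 5% it is 64%. These figures count any such CHF event. Only some would meet both limbs or depend on the scale.

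**The case against.** The row has a coherent reading with no inversion. The parenthesis can be taken to cover every patient who fell below 55% by more than 20%, including one who also went under 40%. The 40% test then serves patients whose baseline was already low. This reading is available, so the inversion is something the wording permits, not something it requires.

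Safeguards apply on every reading: clinical CHF must be controlled, the restart is one dose level lower, and attributable toxicity that has not resolved by 3 weeks ends treatment. These limit the exposure but do not settle the ambiguity. The 3-week rule does not choose between the tests before week 3, and the dose reduction is reversed after two tolerated cycles, with no exception stated for CHF. The section calls its rules guidelines, but they are the only ones a site has for this decision.

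A reader might infer three stronger claims that the documents do not support.
- That the row gives no resume test for these patients. It gives two; what is missing is which one governs.
- That its plain meaning is the easier restart. That is one of several readings.
- That it allows restart below 40%. This would need the within-15% test to govern a patient whose baseline was under 55%. Limb 2 is worded as a reduction below 55%, which naturally means a fall from 55% or more. From there the threshold is at least 55 − 15 = 40% (points) or 0.85 × 55 = 46.75% (relative).

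**Conclusion.** The point stands as an ambiguity in a safety rule. For a patient who meets both limbs, the wording permits restart at 40%. On the limb-matched reading, a smaller fall from the same baseline faces a threshold 10 points (points scale) or 15.25 points (relative scale) higher at a baseline of 65%. That inversion is confined to baselines above 60% in points, or from about 55% on the relative scale if limb 2 means a fall through 55%.

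Few patients would be affected: about half a CHF case is expected among 20 if the earlier rate carries over, and fewer would meet both limbs. The unstated scale is, on its own, a matter of clarification. Overall this is a cheap improvement for patient safety.

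**What to change.** Reword the resume cell so that carfilzomib restarts, one dose level lower, only when all of these hold:
- clinical CHF is controlled;
- LVEF is at least 40%;
- if the patient met the below-55%, more-than-20% criterion, whether or not LVEF also fell below 40%, LVEF is within 15% of baseline.

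Otherwise discontinue. The 3-week rule continues to apply.

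In the same edit, state whether 20% and 15% are LVEF points or relative change. The sponsor should choose. The phrase about baseline value leans relative, while 55 − 15 = 40 fits points. The relative scale is stricter at every baseline below 100%, since 0.80 × B exceeds B − 20 and 0.85 × B exceeds B − 15.

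The cost is one table row. Limb 2 already depends on a baseline LVEF, so the edit relies on no measurement that the row does not already use. The downside is a few longer holds or extra discontinuations. On the relative scale, patients with a baseline of 65% or more would need LVEF above 55% to restart (0.85 × 65 = 55.25).

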6.2.1 Missed Doses

Missed doses will not be replaced. If a subject misses doses of planned therapy due to toxicity, they will resume treatment according to planned schedule once the toxicity is resolved (see above guidelines). If toxicity resolves within the acceptable (+3 day) window surrounding planned therapy, that dose may be administered.

6.2.2 Changes in Body Surface Area (BSA)

Dose adjustments do not need to be made for weight gains/losses of $\leq 20\%$. Subjects with a Body Surface Area (BSA) of greater than 2.2 m^2 will receive a capped dose for a BSA of 2.2 m^2 . Frequency of weight measurement and subsequent recurring calculation of BSA will be done according to institutional guidelines.

6.3 Concomitant medications

6.3.1 Required Concomitant Medications and contraceptive practices

Contraception:

Female subjects of child-bearing potential must agree to use contraception (barrier, hormonal, or intrauterine) for the duration of the study. Male subjects must agree to use a barrier method of contraception for the duration of the study if sexually active with a female of child-bearing potential. Men who have had a prior vasectomy do not need to use a barrier method for contraception.

Antimicrobial prophylaxis:

Subjects should receive antimicrobial prophylaxis according to institutional treatment standards.

6.3.2 Management of prednisone and other immune suppression

Prednisone:

The management of prednisone will be directed by the treating clinician, and dose/duration of prednisone therapy is not mandated by this protocol.

Additional systemic immune-suppressive agents:

It is expected that patients will be on additional systemic immune-suppressive agents at the time of enrollment, and management of those agents is not mandated by this protocol. Other agents can be tapered or discontinued as directed by the treating clinician.

Addition of new systemic immune-suppressive agents while on trial constitutes treatment failure, regardless of the indication for the agent. Systemic immune-suppressive agents include orally or intravenously administered systemically active immune-suppressive drugs, as well as procedures including extra-corporeal photopheresis (ECP).

Treatment failure does not include the following:

1. Adjustment of dosing of existing immune suppressive agents to maintain therapeutic drug levels (e.g. tacrolimus, cyclosporine, sirolimus), as this is standard practice.
2. Adjustment of prednisone dose up or down according to clinical judgment based on clinical manifestations of chronic GVHD and patient tolerance of steroid treatment.
3. Use of topical therapies, including:
 - a. ocular drops or physical interventions (e.g. moisturizing eye drops, ocular cyclosporine drops, punctal plugs, scleral lenses, etc)
 - b. oral rinses or agents (e.g. oral steroid rinse, oral topical immune suppressive agents)
 - c. non-absorbable gastrointestinal steroid agents (e.g. beclomethasone, budesonide)
 - d. topical agents applied to the skin (e.g. topical steroid creams, moisturizing lotion, topical immune suppressive agents such as tacrolimus)
 - e. topical agents applied to the vaginal mucosa (e.g. topical steroid creams or topical immune suppressive agents such as tacrolimus)
4. PUVA
5. Fluticasone, azithromycin, or monteleukast

7 STUDY OUTCOMES

Primary endpoint:

Treatment failure

Treatment failure is the cumulative incidence of addition of systemic immune suppressive therapy, recurrent malignancy, and death. The primary endpoint is 6-month treatment failure.

- See above definitions of systemic immune-suppressive therapy (section 6.3.2)
- Recurrent malignancy – This is defined as hematologic relapse or any unplanned intervention (including withdrawal of immune suppression) to prevent progression of disease in patients with evidence (molecular, cytogenetic, flow cytometric, radiographic) of malignant disease after transplantation.
- The date of this event will be the earlier date of the following:
 - a. Evidence of relapse
 - b. Initiation date of intervention for treatment or prevention of relapse

Secondary endpoints:

Failure-free survival

This time-to-event outcome will be estimated with the composite event of death from any cause, relapse and addition of secondary immune suppressive agents. This will be estimated at 6 months and 1 year.

Overall response rate

Overall response rate (ORR) at 3 and 6 months following initiation of therapy represents the composite outcome of complete and partial response (CR + PR). ORR will be determined by both clinician-defined categories of CR and PR, as well as separately calculated according to the proposed response definitions of the NIH Consensus Conference.¹

Complete response rate

Complete response (CR) at 3 and 6 months following initiation of therapy. CR will be determined by both clinician-defined CR, as well as separately calculated according to the proposed response definitions of the NIH Consensus Conference.¹

Cumulative incidence of non-relapse mortality and primary malignancy relapse

The cumulative incidence of non-relapse mortality (defined as death in the absence of primary malignancy relapse after transplant) and relapse (defined as hematologic relapse or

Carfilzomib for Treatment of cGVHD

any unplanned intervention to prevent progression of disease in patients with evidence (molecular, cytogenetic, flow cytometric, radiographic) of malignant disease after transplantation) will be estimated from time of study therapy initiation. These will be treated as competing-risk events, and estimated at 6 months and 1 year.

Overall survival

Overall survival will be determined from date of study therapy initiation, with death from any cause as the event of interest, and censoring at last follow up date for those with incomplete observations. This will be determined at 6 months and 1 year.

Use of additional systemic immune-suppressive therapies

The use of additional systemic immune-suppressive agents will be captured at each study visit, as this constitutes treatment failure. See above clarification (section 6.3.2) for definitions of systemic immune-suppressive therapies.

Discontinuation of all systemic immune-suppressive therapies

The incidence of complete discontinuation of all systemic immune-suppressive therapies will be determined at 6 months and 1 year.

Treatment success

This endpoint will be estimated at 6 months and 1 year with a composite outcome of complete resolution of all reversible chronic GVHD manifestations, discontinuation of all systemic immune suppressive agents, and freedom from death or primary malignancy relapse after transplant.

Patient-reported outcomes and functional measures

Patients will provide assessment of their functional ability, symptom burden, and quality of life using validated instruments recommended by the NIH Consensus Development Project on Chronic GVHD (2 minute walk test, Lee Chronic GVHD Symptom Scale,² HAP functional scale,³ QOL instruments SF-36⁴ and FACT-BMT⁵). These will be studied at baseline, 6 months, and 1 year.

Biologic studies

These studies aim to discern the biologic impact of proteasome inhibition in the treatment of chronic GVHD. Peripheral blood samples will be obtained at baseline (study enrollment pre-treatment), and then at the 3 and 6 month time points. An additional event-driven blood sample will be obtained when a new systemic immune suppressive therapy is added (treatment failure of carfilzomib).

A total of 15 mL of blood will be drawn at each timepoint, labeled with a study ID and date of draw, and shipped to Moffitt Cancer Center. Samples will be used to confirm effective

Carfilzomib for Treatment of cGVHD

proteasome inhibition. In addition, these samples will be used to perform RNA-sequencing discovery studies for therapeutic response vs. nonresponse, and NanoString nCounter validation of any identified targets. Plasma will be used to conduct ELISAs or other tests to validate potential targets.

8 STUDY DISCONTINUATION

8.1 Criteria for study discontinuation

The following conditions require discontinuation of carfilzomib therapy and termination of study follow up:

1. Patient decision to withdraw from study
2. Death
3. Completion of all study follow up

8.2 Discontinuation of carfilzomib therapy

In the following circumstances, carfilzomib therapy will be discontinued, however study follow up will continue:

1. The treating clinician determines that the patient has responded to therapy and does not require any additional carfilzomib treatment
2. Carfilzomib therapy is discontinued due to unresolved toxicity
3. Carfilzomib therapy is discontinued due to patient non-adherence
4. Carfilzomib therapy is discontinued due to the addition of another line of systemic immune suppressive therapy
5. The patient has relapse of their hematologic disorder or malignancy after transplant

*As described below (section 9.2), AE will be collected until 30 days after the last dose of carfilzomib.

9 ADVERSE EVENTS

For more information about reporting and monitoring adverse events, see the DSMB Charter and the Data Safety Monitoring Plan.

